8.7.1 Complete Response

Tumor/ablation zone disappearance or $\geq 75\%$ decrease in the 1 month baseline sum of the three axes of measurements (longest diameter and the two perpendicular diameters).

Note: If it is the opinion of the investigator that the tumor/ablation zone has likely disappeared, the measurement should be recorded as 0mm. If the tumor/ablation zone is believed to be present and is faintly seen but too small to measure, a default value of 1 mm will be assigned.

8.7.2 Partial Response

Partial response will be defined as $\geq 30\%$ decrease in the 1 month baseline sum of the three axes of measurements (longest diameter and the two perpendicular diameters).

8.7.3 Stable Disease

Stable disease will be defined as $< 30\%$ decrease in the 1 month baseline sum of the three axes of measurements (longest diameter and the two perpendicular diameters), and $< 20\%$ increase of the nadir of the 3 axes of measurements.

8.7.4 Local Failure

Local failure will be defined as $\geq 20\%$ increase in the sum of the three axes of measurements (longest diameter plus the two perpendicular diameters) when compared with the nadir of this 3 axes measurement.

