7.3.3. Cryoablation needle placement

The number and configuration of the needles will be based on the necessity to maintain appropriate distances between adjacent cryoablation needles and anatomic structures, and the final number of needles can only be formulated based upon the configuration of the index tumor(s) at the time of treatment. The use of a single needle per tumor should be avoided as it is well understood there is a benefit to multiple needles as a result of ice coalescence and the potential for increased risk of recurrence. The CT imaging views of the index tumor(s) will enable final assessment of the percutaneous access route and needle placement on the day of the procedure. Cryoablation needles will be placed to create multiple overlapping iceballs to completely cover the index tumor and provide a 5 mm zone of ablation surrounding the index tumor while maintaining appropriate safe distance from the non-targeted tissues (i.e. main bronchus and pulmonary arteries).

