7.7. Months 6, 12, 18 and 24 – Follow-up

Patients will return 6, 12, 18, and 24 months (+/-30 days) post cryoablation procedure. In the event of multiple cryoablation procedure dates, the most recent procedure date will serve as the reference for determining the follow up visit window.

The following assessments will be completed:

- Karnofsky Performance Scale;
- Chest CT scan \pm contrast (contrast is preferred);
- Safety assessment;
- Assessment of metastatic lung disease progression beyond the index tumor and feasibility of treatment;
- Assessment of local tumor recurrence at the index tumor, including additional treatment and feasibility of treatment;
- Assessment of any systemic cancer treatment(s);
- Assessment of any local therapy for the index tumor(s).

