8.7. Response Determination

The month 1 post-ablation CT examination will be used as the reference for determining index ablation zone response at each follow up interval after cryoablation. Sequential follow up intervals will be used to determine local failure.

In the unforeseen circumstance where the patient is unable to complete imaging according to the month 1 follow up visit, the month 3 imaging study may serve as the reference for determining index tumor response at each follow up interval after cryoablation. Every effort should be made to comply with the month 1 imaging requirement.

Efficacy at 12 months post cryoablation will be based on local tumor control that will be separately assessed for each index tumor according to criteria below. Each ablation zone will be evaluated at each time point by measuring its 3 axes (longest diameter and the two perpendicular diameters). For each ablation zone individually, the sum of these three measures will be compared to the 1 month baseline for tumor response and the previous follow up interval imaging study for local failure.

Each ablation zone measurement assessment, along with the overall clinical evaluation of the patient, will be evaluated by an independent imaging panel to assess the final response determinations. This final review can be used in the analysis in the event of 'indeterminate' imaging measurement assessments.

Local Tumor Control will be defined as the absence of local failure.

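### Local failure has only a size criterion, so a recorded local recurrence with less than a 20% rise in the three-axis sum counts as local control

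*Protocol*

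**What the plan says.** The definition of the primary outcome is spread over several sections.

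- **Object measured (Protocol 8.7).** "Each ablation zone will be evaluated at each time point by measuring its 3 axes". The measurement covers the whole ablation zone. Section 7.3.3 plans the ice to cover the tumor and "provide a 5 mm zone of ablation surrounding the index tumor".
- **Failure (Protocol 8.7.4).** A 20% or greater "increase in the sum of the three axes of measurements (longest diameter plus the two perpendicular diameters) when compared with the nadir" of that sum. No other route is given. A marginal nodule, a biopsy result, tracer uptake (FDG-PET-CT is allowed in 8.6) and retreatment are not mentioned as failure.
- **Success (Protocol 8.7).** "Local Tumor Control will be defined as the absence of local failure".
- **Comparator (Protocol 8.7).** This section sets the sum against "the previous follow up interval imaging study for local failure", whereas 8.7.4 uses the nadir.
- **Visit item (Protocol 7.5 to 7.7).** "Assessment of local tumor recurrence at the index tumor, including additional treatment and feasibility of treatment" is required at months 1, 3, 6, 12, 18 and 24. Neither document links it to local failure.
- **Independent review.** Under 8.7 a panel considers the measurements and the clinical picture. Use of its review in the analysis is stated only for indeterminate measurements. Section 16.2 provides a central reader to assess and adjudicate images, without a recurrence criterion.
- **SAP.** The efficacy analysis takes its control criteria from a Section 9.7. The current protocol has no such section, and the criteria are in 8.7. Missing 12-month status is multiply imputed using earlier tumor status, and only local failure at 6 months is carried forward.

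**The concern.** A recurrence at the edge of a treated zone mainly lengthens one axis, while the rule divides that growth by the sum of three. The zone also includes a planned rim of ablated normal lung, which enlarges the denominator. A recurrence can therefore be seen, recorded at a visit and centrally visible while the sum rises by less than 20%. Such a scan can be measured, so it is not indeterminate, and the stated use of the panel's review does not reach it. By definition the tumor is under local control.

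The primary rate is tested against a fixed 84% goal with no control arm to share the error. Each failure missed in this way raises the rate.

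**Working it through.** **1. The plan's own design figure.** Inputs from Protocol 10.1: N = 203, success if 181 or more are controlled, null 0.84, alternative 0.91. With X binomial:

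- P(X ≥ 181 | 203, 0.84) = 0.0239, as stated.
- P(X ≥ 181 | 203, 0.91) = 0.8501, as stated.
- 203 / 0.90 = 225.6, rounded up to 226, as stated.

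**2. Growth needed along one axis.** Let the axes at nadir be a, b and c. If only one axis grows, by g, failure requires

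g ≥ 0.20 × (a + b + c) = 0.60 × mean axis.

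For a round zone of diameter D this is 0.60 × D. Growth of 0.30 × D raises the sum by 10.0%, and 0.50 × D raises it by 16.7%. Neither is a failure.

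**3. In millimetres.** Assume a round zone equal to the tumor plus 5 mm on each side.

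| Tumor | Zone | Growth needed, nadir = full zone | Growth needed, nadir 30% smaller |
|---|---|---|---|
| 10 mm | 20 mm | 12 mm | 8.4 mm |
| 20 mm | 30 mm | 18 mm | 12.6 mm |
| 35 mm | 45 mm | 27 mm | 18.9 mm |

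The last column is 0.60 × 0.70 × zone. It assumes that the rest of the zone then holds its size.

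**4. Dependence on shape and shrinkage.**

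- Elongated zones, growth on the longest axis: for axes 1.25:1:1, 0.20 × 3.25 / 1.25 = 52% of that axis. For 1.5:1:1 it is 47%, and for 2:1:1 it is 40%.
- Perpendicular axes 10% below their nadir-scan values: 3.6 − 2 × 0.9 − 1 = 0.80 × D.
- Zone still shrinking, 21 mm at month 6 and 18 mm at month 12, with a nodule of diameter d touching its edge: the nadir sum is 63 mm, so the sum must reach 75.6 mm. Once d exceeds 18 mm the nodule also sets the perpendicular axes, and 18 + 3d ≥ 75.6 gives d = 19.2 mm.
- Even growth on all three axes needs only 20% on each, so the problem is specific to eccentric growth.

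**5. Effect on the test, as an illustration.** Suppose true control is 84% and a share m of true failures is scored as control. The scored rate is 1 − 0.16 × (1 − m).

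| m (assumed) | Scored rate | P(X ≥ 181 of 203) |
|---|---|---|
| 0 | 0.840 | 0.024 |
| 5% | 0.848 | 0.047 |
| 10% | 0.856 | 0.086 |
| 20% | 0.872 | 0.236 |

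**The case against.** Several points on the other side have force.

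- **Not every recorded recurrence counts as control.** A reader might infer that any recurrence, even one treated again, becomes a success. The documents do not support that. A rise of 20% or more is a failure. Other local therapy to the index tumor leads to withdrawal (7.8), after which missing 12-month status is imputed, with a worst-case sensitivity analysis. Repeat cryoablation restarts follow-up and has its own analysis, and its status in the primary endpoint is not stated.
- **The panel may do more than the text says.** The wording in 8.7 is permissive, and 16.2 mentions adjudication. Even so, no sentence lets either override a measurable rise below 20%.
- **The visit item may only be where failure is recorded.** Section 10.5.5 ties local progression to local tumor failure. That reading is possible, but nothing states it, and it would still leave recurrence below the threshold outside the endpoint.
- **The 60% figure is not a general rule.** It applies to a round zone at nadir size. Shrinkage before the nadir and elongated shapes lower the growth needed, while continuing shrinkage raises it.
- **The probabilities do not describe the SAP's test.** That test is a random-effects logistic model with a Wald bound after multiple imputation. The 181-of-203 rule is the sample-size calculation under independence, and the missed share has no anchor in the documents.
- **Leniency relative to the goal is unknown.** The failure definitions behind the cited rates are not given, so one cannot say that this criterion is easier than theirs. A size rule can also call benign enlargement a failure.

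These points limit the size of the claim. They do not supply the missing rule.

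**Conclusion.** The concern holds in a bounded form. As written, a local recurrence recorded at a visit with less than a 20% rise in the three-axis sum is scored as local control and counts as a primary success. This rests on the text of 8.7, 8.7.4 and 7.5 to 7.7, and on the absence of any linking rule in either document. Recurrences of clinically visible size can fall below the threshold: about 8 to 27 mm of one-sided growth in the round-zone cases shown, depending on zone size and prior shrinkage.

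The resulting bias cannot be estimated from the documents. Under the design's binomial rule, missing one failure in twenty about doubles the 2.4% error and missing one in five takes it to about 24%, but those shares are assumptions. A reader might conclude that the trial would probably meet its goal falsely. The documents do not show that. They show an endpoint definition with a gap whose direct effect is to raise the control rate.

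**What to change.** Amend Protocol 8.7.4 and the SAP endpoint definition, and correct the SAP's reference from 9.7 to 8.7. Score an index tumor as a local failure if either:

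- (a) the three-axis sum rises by 20% or more over nadir; or
- (b) local recurrence at the index tumor is recorded by 12 months and confirmed on the imaging by the central reviewer already provided in 16.2.

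Write the reader's confirmation criteria in advance. Carry a failure by either route forward to 12 months, including when the tumor is then retreated or the patient is withdrawn for other local therapy, so that it is not imputed or reset. Reconcile the comparator in 8.7 (previous scan) with that in 8.7.4 (nadir). Report the sum-only rate as a sensitivity analysis.

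The change uses a visit item and a reader that the trial already has. The cost is a control rate that may be slightly less favorable, a short reading rule to write, and an endpoint that rests partly on reader judgement.

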9. MANUFACTURING, HANDLING AND ACCOUNTABILITY OF STUDY DEVICE AND SUPPLIES

9.1. Manufacturing, Packaging and Labeling

The Galil Medical Cryoablation System and needles are manufactured, packaged and labeled according to current Good Manufacturing Practices (cGMP) and applicable international, national and local regulations, laws, and guidelines.

9.2. Handling and Storage

The Galil Medical Cryoablation System, needles, necessary equipment, and disposables are handled and stored according to Galil Medical's specifications.

9.3. Study Supplies

Study sites will use commercially available device supplies labeled for use specifically for this study. All study supplied devices will be tracked by the sponsor and study site for accountability. A Regulatory Documents binder will be provided to each site. Questionnaires, patient instructions or applicable worksheets will also be provided to each site. The study monitor should be contacted for any issues related to these study supplies.

Cryoablation needles are supplied in individual single use, sterilized packages. Once opened, they should be used immediately for the current procedure or discarded. Cryoablation needles should be stored according to the recommendations on the commercial packaging.

9.4. Recall of Investigational Device

The Galil Medical Cryoablation System and needles are designed and built in accordance to applicable international standards for surgical medical instruments. Any recall of the study device will be done in accordance with applicable international, national and local legislation and guidelines, as well as the sponsor's requirements.

10. STATISTICAL ANALYSIS

This is a prospective, single-arm, phase II study designed to determine the safety and efficacy of Galil Medical's Cryoablation System and needles in cryoablation of metastatic lung tumors.

10.1. Study Design and Sample Size Calculation

This is a prospective, single-arm study designed to determine the safety and efficacy of Galil Medical's Cryoablation System and needles in cryoablation of metastatic lung tumors.

The primary efficacy endpoint for the trial is 12-month local tumor control. The papers shown below were used as reference for clinicians who determined a clinically relevant efficacy endpoint performance goal was 84% success at 12-months.³⁶⁻⁴³ This observed cryoablation rate will be tested against this performance goal.

Paper	Tumors	12-month Local Tumor Control Success	Lower 97.5% 1-sided Wilson CI
Okuneiff (2006)	125	91%	0.8469
Rusthoven (2009)	63	100%	0.9425
Baschnagel (2013)	47	97%	0.8757
Ricardi (2012)	77	94%	0.8632
Norihisa (2008)	43	94.50%	0.8337
Yoon (2006)	101	90%	0.8261

This test is accomplished by testing against the following hypotheses:

$$H_0: C_{\text{DEVICE}} \leq 84.0\%$$

$$H_a: C_{\text{DEVICE}} > 84.0\%$$

The null hypothesis will be rejected and the primary efficacy endpoint performance goal will be met if the lower bound of the exact one-sided 97.5% confidence interval for the six-month closure rate is greater than 84.0%.

PASS 12 was used to calculate the sample size needed. A sample size of 203 tumors achieves 85% power (and guarantees at least 80% power) to detect a difference ($P_1 - P_0$) of 0.0700 using a one-sided binomial test. The target significance level is 0.0250. The actual significance level achieved by this test is 0.0239. These results assume that the population proportion under the null hypothesis is 0.8400.

Power Analysis of One Proportion

Numeric Results for testing $H_0: P = P_0$ versus $H_1: P > P_0$

Test Statistic: Exact Test

Power	N	Proportion Given H_0 (P_0)	Proportion Given H_1 (P_1)	Target Alpha	Actual Alpha	Reject H_0 Beta If $R \geq$ This
0.8501	203	0.8400	0.9100	0.0250	0.0239	0.1499 181

To account for up-to a 10% 12-month tumor attrition rate, the final sample size has been increased to 226 tumors.

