5.1. Primary Endpoint

The primary endpoint for this study is defined as follows:

- Efficacy of cryoablation on local tumor control for each index tumor in patients with pulmonary metastatic disease at 12 months post cryoablation. (See Section 8.7)

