10.5.3. Primary Endpoint

The primary endpoint for this study is defined as follows: efficacy of cryoablation on local tumor control for each index tumor in patients with pulmonary metastatic disease at 12 months post cryoablation.

Patients are allowed up to 6 tumors and the primary efficacy endpoint (tumor control) will be calculated on a per tumor level. To be considered a success each tumor treated during the baseline procedure must meet the tumor control criteria at the 12 month follow-up visit.

The local tumor control counts and rates will be presented along with the 95% two-sided confidence intervals for the rates. The rate numerator will be defined as the number of tumors experiencing tumor control at 12-months. The rate denominator will be defined as the total number of tumors evaluated at 12-months.

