The primary efficacy endpoint for the trial is 12-month local control. The papers shown below were used as reference for clinicians who determined a clinically relevant efficacy endpoint performance goal was 84% success at 12-months. This observed cryoablation group's local control rate will be tested against this performance goal.

Paper	Lesions	12-month Local Control Success	Lower 97.5% 1-sided Wilson CI
Okuneiff (2006)	125	91%	0.8469
Rusthoven (2009)	63	100%	0.9425
Baschnagel (2013)	47	97%	0.8757
Ricardi (2012)	77	94%	0.8632
Norihisa (2008)	43	94.50%	0.8337
Yoon (2006)	101	90%	0.8261

This test is accomplished by testing against the following hypotheses:

$$H_0: C_{\text{DEVICE}} \leq 84.0\%$$

$$H_a: C_{\text{DEVICE}} > 84.0\%$$

where C_{DEVICE} is the observed cryoablation local control rate at 12-months.

The null hypothesis will be rejected and the primary efficacy endpoint performance goal will be met if the lower bound of the one-sided 97.5% confidence interval for the 12-month tumor local control rate is greater than 84.0%.

PASS 12 was used to calculate the sample size needed. A sample size of 203 lesions achieves 85% power (and guarantees at least 80% power) to detect a difference ($P_1 - P_0$) of 0.0700 using a one-sided binomial test. The target significance level is 0.0250. The actual significance level achieved by this test is 0.0239. These results assume that the population proportion under the null hypothesis is 0.8400.

Power Analysis of One Proportion

Numeric Results for testing $H_0: P = P_0$ versus $H_1: P > P_0$

Test Statistic: Exact Test

Power	N	Proportion		Target Alpha	Actual Alpha	Beta	Reject H_0 If $R \geq$ This
		Given H_0 (P_0)	Given H_1 (P_1)				
0.8501	203	0.8400	0.9100	0.0250	0.0239	0.1499	181

To account for up-to a 10% 12-month lesion attrition rate, the final sample size has been increased to 226 lesions.

Note that, for the purposes for sample size calculations, the observations are assumed to be independent. However, the primary analyses will account for within subject correlation, as described below.

General Analysis Methods

Data will be analyzed using descriptive statistics. Continuous variables (e.g., age) will be summarized by the number of patients, mean, standard deviation, median, interquartile range, minimum and maximum. Categorical variables (e.g., race) will be summarized by frequencies and percentages of patients in each category. 95% confidence intervals will be calculated as appropriate.

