Analysis Populations

All primary analyses will be performed on all tumors with a Galil Medical Cryoablation System and needles as the intent-to-treat evaluable population. A supplemental per-protocol analysis

will be done for the primary endpoint, removing tumors that 1) did not have a complete treatment; and subjects who 2) did not meet the study criteria but were enrolled; or 3) had a deviation with high likelihood of affecting the study outcome (as determined by a review of all occurring deviations).

The intent-to-treat and per-protocol analyses will be compared for level of agreement. It is expected that the two populations will be similar; however, any substantial differences between the two will be analyzed appropriately to elucidate the cause of these differences. Missing data will be imputed for the primary analysis as outlined in section "Handling of Missing Data" section later in the SAP. Additional sensitivity analyses using alternate missing data imputation will be presented.

Efficacy Endpoint Analysis

Efficacy Endpoint

The primary efficacy endpoint for this study is assessment of cryoablation on local tumor control in patients with pulmonary metastatic disease at 12 months post cryoablation.

Analysis Methods

The primary efficacy endpoint for this study is defined as follows: local tumor control in patients with pulmonary metastatic disease at 12 months post cryoablation. Tumor control will be defined by the criteria defined in Section 9.7 of this protocol.

Patients are allowed up to 6 tumors and the primary efficacy endpoint (tumor control) will be calculated on a per tumor level.

The rate of local tumor control at 12-months will be analyzed using a random effects logistic regression model accounting for within subject correlation to account for multiple tumors per subject. The null hypothesis will be tested comparing the lower bound of the Wald 97.5% one-sided confidence interval for the estimated rate of local tumor control to the performance goal of 84.0%. If the lower bound is greater than 84.0%, the null hypothesis will be rejected and the endpoint will be considered met.

Safety Endpoint Analysis

Safety Endpoint

The safety endpoint for this study is to assess the incidence and severity of cryoablation related adverse events.

Analysis Methods

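### The protocol's success rule names a six-month closure rate and an exact interval, while the endpoint is 12-month local tumor control and the SAP tests a Wald bound

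*Protocol*

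**What the plan says.** Protocol section 10.1 opens by stating that "The primary efficacy endpoint for the trial is 12-month local tumor control" and sets the 84% performance goal at 12 months. After the hypotheses, it says the null hypothesis is rejected and the goal met if the "lower bound of the exact one-sided 97.5% confidence interval for the six-month closure rate is greater than 84.0" percent. The power table in the same section gives an exact one-sided binomial test with 203 tumors and rejection at 181 or more successes.

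The other protocol sections agree on the outcome and its time. Section 5.1 places local tumor control "in patients with pulmonary metastatic disease at 12 months post cryoablation". Section 8.7 defines local tumor control as absence of local failure and sets efficacy at 12 months. Section 10.5.3 says each treated tumor "must meet the tumor control criteria at the 12 month follow-up visit". Month 6 appears in section 7.7 as one of several follow-up visits: "Patients will return 6, 12, 18, and 24 months".

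The SAP, under Sample Size Justification, requires that the "lower bound of the one-sided 97.5% confidence interval for the 12-month tumor local control rate is greater than 84.0" percent, with no interval type named. Under Efficacy Endpoint Analysis it specifies a random effects logistic model and compares the "lower bound of the Wald 97.5% one-sided confidence interval for the estimated rate of local tumor control" with 84.0%. Its revision history says the word exact was dropped because the final test is the random effects model.

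**The concern.** The sentence in section 10.1 is the decision rule for the trial's one formal hypothesis test, and it departs from the rest of the plan in two ways.

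First, it names an outcome that is defined nowhere (closure) and a time (six months) at which no endpoint is set. Nobody could carry it out as written.

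Second, it specifies an exact interval, while the SAP specifies a model-based Wald bound. These are different tests. If the result lands near the pass mark, the protocol's rule and the SAP's rule could give opposite answers, and neither document says which prevails. The SAP's supportive weighted average response also reports a 95% exact interval on pooled lesions. The lower limit of an equal-tailed interval of that kind is the bound in the protocol's rule, so a disagreement could be visible in the trial's own tables.

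**Working it through.** **Inputs.** From protocol section 10.1: null rate 0.84, alternative 0.91, n = 203, rejection at R ≥ 181, target alpha 0.025, 10% attrition. From protocol section 5: 226 tumors in about 150 patients. The within-patient correlation (ICC) is not given in either document, so a range of 0.1 to 0.5 is assumed.

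**1. Reproduce the plan's figures.**
- Alpha = P(X ≥ 181 | n = 203, p = 0.84) = 0.0239, as stated.
- Power = P(X ≥ 181 | n = 203, p = 0.91) = 0.8501, as stated.
- Attrition: 203 / 0.90 = 225.6, rounded up to 226, as stated.
- The exact (Clopper-Pearson) one-sided 97.5% lower bound is 0.8405 at 181/203 (pass) and 0.8349 at 180/203 (fail).

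The sizing is thus an exact test of a proportion against the 84% goal, which section 10.1 sets at 12 months. Replacing the six-month closure wording leaves every one of these numbers unchanged.

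**2. Pass mark under a Wald bound, no clustering.** Write p = R/203.
- Probability scale: p − 1.96 × √[p(1 − p)/203]. At R = 180, p = 0.8867 and the bound is 0.8867 − 1.96 × 0.02225 = 0.8431 (pass). At R = 179 it is 0.8374 (fail). The pass mark is 180, and P(X ≥ 180 | 203, 0.84) = 0.0384.
- Logit scale: ln[R/(203 − R)] − 1.96 × √[1/R + 1/(203 − R)], compared with ln(0.84/0.16) = 1.658. At R = 181: 2.107 − 1.96 × 0.2258 = 1.665 (pass; back-transformed 0.8409). At R = 180: 2.057 − 1.96 × 0.2214 = 1.623 (fail; 0.8353). The pass mark is 181.

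**3. Pass mark with assumed clustering.** Mean tumors per patient m = 226/150 = 1.51. The variance is multiplied by the design effect 1 + (m − 1) × ICC.

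| Assumed ICC | Design effect | Wald, probability scale | Wald, logit scale | Exact |
|---|---|---|---|---|
| 0 | 1.00 | 180 | 181 | 181 |
| 0.1 | 1.05 | 180 | 182 | 181 |
| 0.2 | 1.10 | 180 | 182 | 181 |
| 0.3 | 1.15 | 181 | 182 | 181 |
| 0.5 | 1.25 | 181 | 183 | 181 |

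The exact column does not move because that rule treats tumors as independent. The design effect stands in for the fitted random effects model, so the clustered marks are approximate.

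**The case against.** The strongest reply is that the closure phrase is an obvious slip. The same section names the 12-month endpoint, sets the goal at 12 months, uses a table of 12-month control rates, inflates for 12-month attrition and prints a count rule of 181 out of 203. The SAP, which governs the analysis, already has the right outcome and time. Its move away from an exact interval is logged with a sound reason: a binomial interval ignores several tumors in one patient. All of this stands. It makes the slip unlikely to misdirect the analysis, but it does not make the sentence correct or settle which interval decides.

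A reader might go further and infer that the rule would be applied to six-month control data and would pass far too easily. Under a constant failure hazard, 84% control at 12 months is √0.84 = 91.7% at six months, and P(X ≥ 181 | 203, 0.9165) is 0.916 instead of 0.0239. If 70% or 30% of 12-month failures occur by month 6, the six-month rates are 1 − 0.7 × 0.16 = 0.888 and 1 − 0.3 × 0.16 = 0.952, and the probabilities are 0.491 and above 0.999. The arithmetic is right, but the documents do not support the reading. It keeps six months while replacing closure with local control, a combination that appears nowhere. It also needs control to fall steadily with time. That is not assured, because section 10.5.3 counts only tumors evaluated at 12 months, while section 7.8 withdraws patients given other local treatment to an index tumor and restarts follow-up for retreated tumors.

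It would likewise be too strong to say that month 6 plays no part in the trial. It is a scheduled CT visit, just not an endpoint time.

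**Conclusion.** The concern holds as an error in a stated decision rule plus an unreconciled difference between protocol and SAP. The outcome and time in section 10.1 are wrong as written; the intended ones are clear from the context, and no sizing figure is affected.

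The interval conflict is the part that could change a result, and it is modest in size. At 203 tumors the pass mark is 181 under the exact rule and 180 to 183 under the Wald rule, depending on the unstated scale and an assumed ICC from 0 to 0.5. The least favorable case for error control is the probability-scale Wald bound with independent tumors, where alpha is 0.0384 against the 0.025 target. The 92% false-pass probability describes only the literal six-month reading and should not be given as the expected harm.

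These figures rest on 203 evaluated tumors, on 1.51 tumors per patient, and on the design-effect approximation.

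**What to change.** 1. In protocol section 10.1, replace *six-month closure rate* with *12-month local tumor control rate*.
2. Name one primary test, in the same words, in protocol section 10.1 and in both SAP places that state the rule. If it is the SAP's random effects Wald bound, state the scale on which the interval is built, preferably logit. Without clustering, the logit scale reproduces the 181 pass mark, while the probability scale gives 180 and exceeds the alpha target.
3. Add a sentence to both sample size sections saying that 203, 181, 0.0239 and 0.8501 belong to an exact test on independent tumors. Copying the SAP's interval into the protocol without this note would leave the power table describing a different test from the one in the rule. The SAP already states that independence was assumed for sizing; the protocol does not.

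The cost is a few sentences in a protocol amendment and matching SAP edits. No sample size figure, visit or data collection changes.
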